As in Part 1, at the Week 4 visit participants will have safety assessments to evaluate suitability to receive the second vaccination as outlined in Section 4.2.2. Participants with any of the following conditions will not be eligible to receive a second vaccine dose:

- Positive pregnancy test at Day 29 (female participants),
- Occurrence of any possibly, probably or definitely treatment-related Grade 3 or 4 AE or SAE following the initial vaccination
- Occurrence of any Grade 3 or 4 AE or SAE following the initial vaccination without plausible alternative explanation
- Presence of acute illness or significant new medical condition including positive SARS-COV-2 rapid molecular test prior to dosing

Participants deemed ineligible due to presence of acute illness or new medical may be reassessed during the visit window (+7 days), and if the condition resolves, may have a second vaccination within 1 week of their scheduled Week 4 Visit. In such situations the Principal Investigator must contact the study Medical Monitor and gain consensus on the decision to continue participant with study vaccinations prior to administration of the second dose.

Following completion of the Active Period (Week 8 visit) participants will continue to be monitored for SAEs, MAAEs and for exposure to and/or symptomatic COVID-19 through Month 13/EOS during the study Safety Follow-up Period. In addition, these participants will be evaluated for immunogenicity as specified in the SoA (Table 4).

Any participant who discontinues study drug early (does not receive the second dose) will enter the Safety Follow-up Period a month earlier at Week 4 and will be monitored for safety and exposure to and/or symptomatic COVID-19 as described above, and complete immunogenicity assessments through EOS per the SoA (Table 4).

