SARS-CoV-2 rapid Ab test ^a	X	Х							a. Test to be repeated at Day 1 only if Screening test completed >7 days prior to the Day 1 Visit.
Nasal Swab for SARS-CoV-2 (RT-PCR)		X							Collect swab predose at Day 1. Collect swab at any time during the study if participant reports symptoms and/or exposure to COVID-19. If test positive, collect samples at 2-day intervals until a negative test result is observed.
Vaccination		X		Xb					b. Participants must be assessed for suitability for 2^{nd} dose, per Section 4.2 . If they are not eligible for their 2^{nd} dose, participants will enter the Safety Follow Up period at Week 4.
Dispense Solicited Symptom Diary		Х		Х					
Review & Collect Solicited Symptom Diary			Х		Х				
Review Prior & Concurrent Medication	Х	Х	Х	Х	Х	Х			
Query for TEAEs, SAEs and MAAEs		Х	Х	Х	Х	Х	Xc	Xc	c. Only SAEs and MAAEs will be collected during the Safety Follow-up Period.
Query for exposure to and/or Symptoms of COVID-19 ^d		Х	Х	Х	Х	Х	Х	Х	d. Unscheduled visit must be completed if participant reports symptoms or exposure to COVID-19.

Immunogenicity Assessments							
SARS-CoV2-specific IgG/IgA (serum)	Xe		Х		X	Х	e. An aliquot of serum collected at baseline will be stored for testing (e.g. PF4 antibody ELISA) should an AES related to blood clots be reported anytime during the study period.
Neutralizing Ab to SARS-CoV-2 (serum)	Х		Х		Х	Х	
Fixed whole blood	Х	Х	Х	Х			Additional exploratory immunoassays
Nasal swab for antigen S-specific IgA	Х		Х		Х	Х	
Saliva sample for antigen S-specific IgA	Х		Х		Х	Х	

Abbreviations: Ab, Antibody; ; COVID-19, coronavirus disease 2019; Cytof, Mass cytometry; EOS, End of Study; ET, Early Termination; HBV, Hepatitis B Virus; HCV, Hepatitis C Virus; HIV, Human Immunodeficiency Virus; ICC, intracellular cytokine cytometry; IgA, immunoglobulin A; IgG, immunoglobulin G; MAAE, medically attended adverse events; NP, Nasopharyngeal; PBMC, peripheral blood mononuclear cells; RT-PCR, reverse transcription polymerase chain reaction; SAE, serious adverse event; SARS-CoV-2, severe acute respiratory syndrome coronavirus 2; TEAE, treatment-emergent adverse events; WOCBP, women of childbearing potential; PF4, platelet factor 4.

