4.3. Part 2 Eligibility Criteria

4.3.1. Part 2 Inclusion Criteria

To be eligible for this study, participants must meet all of the following criteria:

Age

1. 18 - 75 years of age (inclusive) at the time of signing the ICF.

Type of Participants

- 2. Negative for current or prior SARS-CoV-2 infection (tested using a rapid antibody test) at screening and within 7 days prior to the Baseline visit.
- 3. In stable and good health, without significant medical illness, based on medical history, physical examination, vital signs, and clinical laboratory tests as determined by the Investigator.
- 4. Safety laboratory values within the range of normal for platelet counts² and the following coagulation tests: PT/INR, aPTT and fibrinogen
- 5. BMI between 17 and 32 kg/m² at screening.
- 6. Capable of providing signed informed consent.
- 7. Available for all planned visits and phone calls, and willing to complete all protocoldefined procedures and assessments (including ability and willingness to swallow multiple small enteric-coated tablets per vaccine dose).

Gender and Reproductive Considerations

8. Male or female participants.

Contraception use by men or women should be consistent with local regulations regarding the methods of contraception for those participating in clinical studies. Refer to Appendix 4 (Section 9.4).

- 9. Female participants must not be breastfeeding and must have a negative pregnancy test at screening and before each vaccination and fulfill one of the following criteria:
 - a. At least 1 year post-menopausal (defined as amenorrhea for ≥12 consecutive months prior to Screening without an alternative medical cause).

Women under 60 years will need to verify post-menopausal status via a folliclestimulating hormone (FSH) test if another option to prevent potential pregnancy will not be utilized for 30 days prior to baseline vaccination and until 60 days after the last vaccination.

- b. Surgically sterile
- c. Use of oral, implantable, transdermal or injectable contraceptives for 30 days prior to initial vaccination and until 60 days after the last vaccination.

² If platelets are abnormal, a normal NaCitrate platelet test is needed.

- d. A reliable form of contraception must be approved by the Investigator (e.g., double barrier method, Depo-Provera, intrauterine device, Norplant, oral contraceptives, contraceptive patches).

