7.1.1. SARS-CoV-2 Infection and COVID-19 Diagnosis

Participants will be monitored for SARS-CoV-2 infection and/or symptomatic COVID-19 in the following manner:

- Testing for prior exposure by rapid antibody (Ab) test at Screening and Baseline (prevaccination) if Screening test >7 days prior to Baseline Visit (**Part 1 Cohort 1 only**).
- Testing by an FDA authorized rapid molecular test at any time a participant reports illness compatible with COVID-19 or reports known/ possible exposure to COVID-19. A sample will also be collected at Baseline to test for potential of pre-dose exposure should confirmation of negative infection be needed in participants who contract COVID-19 during the study.
- A negative onsite rapid molecular test is required prior to dosing at Days 1 and 29. This testing is needed given the high rates of COVID-19 being observed at clinical sites with the spread of Omicron variant.

Any participant reporting COVID-19 like illness or exposure to COVID-19 during the study will be asked to return to the site for an unscheduled visit to test for SARS-CoV-2 infection. Any FDA authorized rapid molecular test (e.g. LUCIRA COVID-19 Test) may be used for home or on-site testing for monitoring COVID-19 infection.. Participants with confirmed SARS-CoV-2 infection at any time during the study period will be asked to provide a nasal sample for rapid molecular test every two days after their confirmatory test until they test negative. The duration of q2day testing should end after 10 days if still testing positive at that time. They will also be monitored for clinical disease duration, severity, and outcome. The participant will be counseled

to notify their Primary Care Physician of their positive SARS-CoV-2 status and seek medical care should they become symptomatic.

The occurrence of virologically confirmed (by polymerase chain reaction [PCR] or rapid molecular test to SARS-CoV-2) symptomatic mild, moderate, or severe COVID-19 is defined in Table 5.

Subjects with confirmed COVID-19 will be evaluated for severity of disease as well as for the potential for vaccine-associated enhanced disease (VAED).

Mild	 At least one or more of the following: Fever (defined by subjective or objective measure, regardless of use of anti-pyretic medications)
wind	 New onset cough ≥ 2 COVID-19 respiratory/non-respiratory symptoms in Table 6 AND Does not meet criteria for moderate or severe disease

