8.3.2. Part 2- Double Blind, Placebo Controlled

Endpoint	Statistical Analysis Methods
Primary: 1. Primary Efficacy	All analyses will be performed at 6 months post last vaccination. The database will be locked and unblinded at this time the efficacy and safety analysis will be conducted.
2. Secondary Efficacy	The evaluable efficacy population will be the primary analysis population for all efficacy analyses. Additional analyses based on the all-available efficacy population will be performed.
3. Safety	1. Primary Efficacy
	Frequency of virologically confirmed COVID-19 illness and serologically confirmed SARS-CoV-2 infection occurring from 7 days following second study drug dose administration.
	Ratio of confirmed COVID-19 illness from 1 week after the Dose 2 per 1000 person-years of follow-up in participants without evidence of infection for the active vaccine group to the placebo group VE will be estimated by $100 \times (1 - IRR)$, where IRR is the calculated ratio of confirmed COVID-19 illness per 1000 person-years follow-up in the active vaccine group to the corresponding illness rate in the placebo group from 1 week after the Dose 2.
	VE will be analyzed using a beta-binomial model. After the above objective is met, the second primary endpoint will be evaluated as below. Ratio of confirmed COVID-19 illness from 1 week after the Dose 2 per 1000 person-years of follow-up in participants with and without evidence of infection (prior to 1 week after

Vaxart,	Inc.
---------	------

receipt of Dose 2) for the active vaccine group to the placebo group VE will be estimated by $100 \times (1 - IRR)$, where IRR is the calculated ratio of confirmed COVID-19 illness per 1000 person-years follow-up in the active vaccine group to the corresponding illness rate in the placebo group from 1 week after the second dose. VE will be analyzed using a beta-binomial model.
The efficacy analysis for the first primary objective evaluation will be based on the participants without evidence of infection before vaccination and included in the evaluable efficacy population and in the all-available efficacy population.
The efficacy analysis for the second primary objective evaluation will be based on all participants included in the evaluable efficacy population and in the all- available efficacy population.

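### Section 7.1.1 provides for testing the Part 2 Day 1 swab only after later COVID-19, so if the swab counts as evidence of infection, the first primary analysis set depends partly on outcome and judgement

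*Combined protocol and SAP*

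**What the plan says.** **The swab.** Table 4 (section 1.2) has a Day 1 RT-PCR row for all Part 2 participants: "Collect swab predose at Day 1". Section 7.1.1 gives the baseline sample's purpose: to test for pre-dose exposure "should confirmation of negative infection be needed in participants who contract COVID-19 during the study". No section says that all swabs are assayed, who judges need, or when.

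**The analysis set.** In section 8.3.2 the first primary objective is analysed in "participants without evidence of infection before vaccination and included in the" evaluable efficacy population, and also in the all-available efficacy population. The second primary objective uses all participants in those populations and is evaluated only after the first is met. The section names no test that counts as evidence of infection. It also gives two windows: one ends at vaccination, and the other, in the wording of the second endpoint, ends one week after dose 2.

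**The other baseline tests.**
- *Rapid antibody test.* Part 2 inclusion criterion 2 (section 4.3.1) requires participants to be "Negative for current or prior SARS-CoV-2 infection (tested using a rapid antibody test) at screening", and Table 4 schedules the test. Section 7.1.1 lists "Testing for prior exposure by rapid antibody (Ab) test at Screening and Baseline" but restricts it to Cohort 1 of Part 1.
- *Rapid molecular test.* Section 7.1.1, without limiting it to either Part, says "A negative onsite rapid molecular test is required prior to dosing at Days 1 and 29". The Part 2 synopsis bars a second dose for "Presence of acute illness or significant new medical condition including positive SARS-COV-2 rapid molecular test prior to dosing". Table 4 has no row for this test (Table 3, for Part 1, does), and section 4.2.2 leaves it out of the Week 4 assessments and the second-dose criteria.
- *Serum.* Table 4 collects Day 1 serum for SARS-CoV-2 IgG/IgA and neutralizing antibody from everyone.

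**The concern.** Membership of a primary analysis set should rest on baseline data measured the same way in everyone. If the Day 1 swab is part of the evidence, a swab-positive participant who later becomes a case can be taken out, while a swab-positive participant who does not is never assayed and stays in the person-time. This applies to infections that the entry tests miss.

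Two things are at stake. Events leave the numerator while comparable person-time stays in the denominator, so both arms' rates are understated. And the plan does not say who decides that confirmation is needed, or whether that person is blinded. Section 5.4.3 blinds investigators and sites but gives some sponsor representatives unblinded assignments for purposes that include bioanalytical analysis. With very few vaccine-arm cases expected, one discretionary assay could move the headline estimate. The contrast between the two primary objectives, which differ only by infection status, is also blurred when that status is undefined and unevenly measured.

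**Working it through.** **Inputs.** Section 8.1.2: attack rate in the unvaccinated 5%, VE 90%, two-sided alpha 0.05, 95% power, 341 per arm, 800 randomized. Section 5.4.2: 1:1 allocation. Section 4.2.4: about 6 months of efficacy follow-up. Section 8.3.2: VE = 100 × (1 − IRR).

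**The plan's own figure.** With p₁ = 0.05, p₂ = 0.005 and mean 0.0275, the pooled-variance formula gives

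n = [1.960 × √(2 × 0.0275 × 0.9725) + 1.645 × √(0.05 × 0.95 + 0.005 × 0.995)]² / 0.045² = (0.4533 + 0.3768)² / 0.002025 ≈ 340.3, rounded up to 341.

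The stated sample size reproduces and is not in dispute.

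**Check 1: every case is assayed under blind.** Assumptions not in the documents: a share q of participants is swab-positive after the entry tests; their attack rate is 0.2 to 5 times that of swab-negatives; VE in them is either 0 or 90%; cases contribute half the follow-up time on average.

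Worked example, q = 5%, same attack rate and VE in swab-positives, 341 per arm, 0.5 years:
- Placebo, all positives removed: 0.05 / (0.95 × 0.5 + 0.05 × 0.25) = 0.05 / 0.4875 = 102.6 per 1000 person-years.
- Placebo, only positive cases removed: 16.20 cases / (157.93 + 8.10 person-years) = 97.6. The 8.10 is the retained person-time of swab-positive non-cases (17.05 × 0.95 × 0.5).
- Vaccine: 10.03 with all positives removed; 1.62 / (161.57 + 8.48) = 9.53 with only positive cases removed.
- VE: 1 − 10.03/102.6 = 90.23% against 1 − 9.53/97.6 = 90.24%.

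Over the whole range of assumptions:

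| q | VE, all positives removed | VE, only positive cases removed | Placebo rate per 1000 person-years (102.6 if all removed) |
|---|---|---|---|
| 1% | 90.23% | 90.22–90.25% | 101.5–101.8 |
| 5% | 90.23% | 90.21–90.33% | 97.4–98.6 |
| 10% | 90.23% | 90.20–90.43% | 92.2–94.5 |

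The swab precedes dosing under 1:1 randomization, so the distortion nearly cancels in the ratio. It does not cancel in the rates, which fall by roughly q.

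**Check 2: single cases are assayed selectively.** Expected cases with 400 per arm: 400 × 5% = 20 placebo and 20 × (1 − 0.90) = 2 vaccine. VE = 1 − v/p, with Clopper-Pearson limits on v/(v + p), assuming equal person-time:
- 2 v 20: 90.0% (95% CI 58.8 to 98.9)
- 1 v 20 (one vaccine case removed): 95.0% (68.7 to 99.9)
- 2 v 19 (one placebo case removed): 89.5% (56.4 to 98.8)

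With 341 per arm (17.05 and 1.7 expected, taken as 2 v 17), removing one vaccine case moves VE from 88.2% to 94.1%.

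**The case against.** **Other pre-dose tests apply whatever the outcome.** The entry antibody test covers all Part 2 participants under criterion 2 and Table 4. Section 7.1.1 also demands a negative rapid molecular test before each dose, and the evaluable population is limited to eligible participants, cases and non-cases alike. This stands in large part. A reader might infer that infected non-cases are never removed, or that nearly all baseline-infected participants would stay in the set; the documents support neither. The remaining gap is infections that these tests miss, and it is wider if the molecular test does not apply in Part 2, which the passages leave unclear.

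**Section 7.1.1 may be written for Part 1, in which case Table 4 governs.** Table 4 sets no outcome condition on the Day 1 swab, and its note about repeat sampling after a positive test could be read as assuming a result. But Table 4 speaks of collection ("Collect swab predose at Day 1. Collect swab at any time during the study if participant reports symptoms and/or exposure to COVID-19") and does not say that every Day 1 swab is assayed. If Table 4 is meant to govern, that should be stated.

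**Nothing makes the swab the criterion, and section 8.3 leaves the populations to the SAP.** This stands, and it makes the concern conditional. A reader might infer that the set is decided by the outcome; the documents do not go that far.

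**Antibody baseline.** A reader of section 7.1.1 alone might infer that Part 2 has none. Criterion 2, Table 4 and the Day 1 serum assays contradict that.

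**The single-case example is improbable under blind.** At 1–5% positivity and equal attack rates, 0.02–0.10 of the two vaccine cases would be swab-positive, a 2–10% chance that either is. Fair. It illustrates sensitivity to discretion, not an expected bias. The second primary objective's set does not depend on infection status.

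**Conclusion.** The point holds in a conditional form. Section 7.1.1 links testing of the baseline sample to later COVID-19 and to an undefined need, and no passage requires assay in everyone. If the swab counts towards absence of infection before vaccination, part of the first primary set depends on outcome and judgement, for infections that the entry tests miss.

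A biased VE is a tempting inference, but the arithmetic does not support it when every case is assayed under blind: the shift is at most 0.2 points at the planned 90% VE, for assumed positivity of 1–10%. What remains is incidence understated by roughly the share of swab-positives (placebo 102.6 to about 98 per 1000 person-years at 5%), and exposure to selective removal of single cases (90% to 95% in the 2 v 20 example). The prevalence, relative attack rates and VE in swab-positives are assumptions.

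The contradictions over the antibody test, the pre-dose molecular test and the two windows are plain on the page and need no assumption. This is a low-cost improvement worth making; it does not undermine the design or the sample size.

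**What to change.** 1. In sections 7.1.1 and 8.3.2, state that the Day 1 swab of every randomized Part 2 participant is assayed by RT-PCR, blinded to arm and case status, before database lock.
2. In section 8.3.2, define absence of evidence of infection by named tests and dates, applied alike to cases and non-cases. Give one window, resolving the one that ends at vaccination against the one that ends a week after dose 2.
3. Extend the antibody bullet in section 7.1.1 to Part 2, to agree with Table 4 and inclusion criterion 2.
4. Reconcile the Part 2 synopsis, section 4.2.2, section 7.1.1 and Table 4 on the pre-dose rapid molecular test. Which version should govern dosing is for the sponsor to settle.

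Cost: about 800 batched RT-PCR assays on swabs already collected, and a few sentences of text. No new visits or samples are needed for steps 1 to 3; whether step 4 adds a test depends on how it is resolved.

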7.1.2. Immunogenicity

Samples will be collected from all participants for immunogenicity assessment according to the time points specified in the SoA (Section 1.2; Table 3 and Table 4). The following immunoassays will be performed:

Key immunogenicity assessments:

Part 1:

- SARS-CoV2-specific IgG/IgA by MSD (Serum)
- Neutralizing antibody titers to SARS-CoV-2 (Serum)

Part 2:

- SARS-CoV2-specific IgG/IgA by MSD (Serum)
- Neutralizing antibody titers to SARS-CoV-2 (Serum)

Additional Immunogenicity Assessments:

Part 1:

- T cell responses by intracellular cytokine cytometry (ICC)
- Antigen S-specific IgA (Nasal Swabs)

- Antigen S-specific IgA (Saliva)
- Anti Ad5 antibodies (optional), (Serum)

Part 2:

- Antigen S-specific IgA (Nasal Swabs)
- Antigen S-specific IgA (Saliva)

Additional exploratory immunoassays may also be run to further characterize the immune response of the VXA-CoV2-1.1-S vaccine. Sample collection, processing and shipping details are provided within the General and Immunogenicity Laboratory Manuals.

7.2. Safety Assessments

The safety of VXA-CoV2-1.1-S will be evaluated through the reporting of solicited symptoms of reactogenicity for 1 week following each study drug administration, unsolicited TEAEs for 4 weeks following each study drug administration, and SAEs and MAAEs including AESIs, NOCIs for up to 56 weeks following the first vaccine dose. Because the VXA-CoV2-1.1-S vaccine contains a double-stranded RNA (dsRNA), adjuvant MAAEs will be collected through one year post last dose to address the theoretical potential for induction of autoimmune or auto-inflammatory diseases, as is standard for this class of vaccines. The conditions listed in Appendix 5 (Section 9.5), as well as any other unexpected medical conditions requiring medical attention will be monitored during the Safety Follow-up period. Subjects will also be monitored for exposure to SARS-CoV2 and symptomatic SARS-CoV2 infection (COVID-19) as noted in section 7.1.1. Subjects with symptomatic COVID-19 will be further evaluated for severity of disease and the potential for VAED.

Planned time points for all safety assessments are provided in the SoA.

7.2.1. Physical Examination

A complete physical examination will include, at a minimum, assessments of the skin, cardiovascular system, respiratory system, abdomen (gastrointestinal, liver and spleen) and neurological system. Height and weight will also be measured and recorded at Screening.

A targeted, symptom-directed physical examination will include, at a minimum, assessments of the skin, respiratory system, cardiovascular system, and abdomen (liver and spleen).

7.2.2. Vital Signs

Blood pressure, heart rate, and respiratory rate will be measured after the participant has been resting for 5 minutes. Vital signs will be measured prior to any blood draw that occurs at the same timepoint.

7.2.3. Clinical Safety Laboratory Assessments

- See Appendix 2 (Section 9.2) for the list of clinical laboratory tests to be performed and to the SoA for the timing and frequency.
- The Investigator must review the laboratory report, document this review, and record any clinically relevant changes occurring during the study in the AE section of the eCRF. The laboratory reports must be filed with the source documents.
- All laboratory tests with values considered clinically significant during participation in the study or within 14 days after the last dose of study drug should be repeated

until the values return to normal or baseline or are no longer considered clinically significant by the Investigator or Sponsor's Medical Monitor (or designee). If such values do not return to normal/baseline within a period of time judged reasonable by the Investigator, the etiology should be identified, and the Sponsor notified.

- Laboratory values which are abnormal AND lead to either the requirement for an intervention, the requirement for additional medications, or are felt to otherwise be medically important should be recorded as adverse events in the eCRF. Only abnormal labs that are clinically significant, per the judgement of the investigator, should be reported as treatment-emergent adverse events, which should be graded based on the clinical scenario. Further, the grading of these adverse events should be based on guidance provided in protocol Section 9.3.4.1 Grading the Severity of TEAEs.
- Hematology or serum chemistry parameters will be graded according to the FDA toxicity grading scale (Section 9.3.4.1.2) and will be adjusted to align with local laboratory reference ranges (Part 1 only) for clinically significant abnormal laboratory tests. Subjects have the ability to rescreen once should screening values fall outside of the allowed eligibility criteria, per the discretion of the Investigator. Post-screening abnormal lab results with toxicity grade 3 or above that are deemed not clinically significant by the investigator and not captured as adverse events will be included separately in the clinical study report.
- Pregnancy testing should include serum hCG at screening. Negative urine pregnancy test should be confirmed on Days 1 and 29 prior to dosing..

